#### 2.3.4 Pharmacokinetic Endpoints

The pharmacokinetic endpoint is plasma MF concentrations at 1 hour (±10 minutes) post study treatment administration and at Days 2 or 3, Days 5 or 8, and Weeks 4, 12, 16 or 20, 24, and 25/Follow Up.

#### 3 STATISTICAL METHODOLOGY

#### 3.1 General Considerations

Unless otherwise specified, the efficacy data will be presented separately for Part 1 and Part 2 as Part 1 is not randomized and does not include a placebo arm. The efficacy data from Part 1 will be descriptively summarized by arms (LYR-220-16 and LYR-220-32) without statistical testing. The safety data will be presented combining data from both Part 1 and Part 2. Specifically, the safety data from the subjects who received LYR-220-32 in Part 1 will be combined with the subjects who received LYR-220-32 in Part 2 in order to assess the totality of safety of LYR-220-32 from the study. The safety data from the subjects who received LYR-220-16 in Part 1 and from the subjects who received sham in Part 2 will be summarized without combining with the other arms (i.e., LYR-220-16 from Part 1, LYR-220-32 combining Part 1 and Part 2, and sham from Part 2).

### 3.1.1 Analysis Day

Analysis day for analysis visit windows (i.e., "Aday") will be calculated from the date of study treatment (LYR-220 or sham) administration. The day of study treatment administration will be Aday 1, and the day immediately before Aday 1 will be Aday -1.

Additionally, analysis day relative to the last dose day (i.e., "Aenday") will be calculated from the date of last dose of study treatment. The day of last dose of study treatment will be Aenday 0, and the day immediately after Aenday 0 will be Aenday 1. Data collected up to 31 days after end of treatment will be included in the analysis.

## 3.1.2 Analysis Visits

Analysis visits will be used for efficacy and safety endpoint analysis. Follow up visits are defined as any visits during 1 day and up to 31 days after end of treatment. Scheduled visits will be assigned to analysis visits as recorded on the Case Report Form (CRF) if they are within the corresponding analysis visit windows described in the tables below. Scheduled visits that do not fall in the corresponding analysis visit windows are considered unscheduled visits when assigning analysis visits. In order to maximize the data available for assessments with regular scheduled visits, where possible, results from unscheduled visits will be assigned to analysis visits according to the following visit windows. When multiple visits are within the same analysis visit window, the one closest to the target day will be used. For efficacy endpoints, if two values are equally distanced, select the value before the target day.

If both paper-based patient-reported outcomes and ePRO are completed at the same day, ePRO will be used for analysis.

If multiple ePRO are completed at the same day and the input are different, the entry having the worst total score will be used for analysis. If multiple ePRO are completed at the same day and the input are identical, the earliest entry will be used for analysis.

An unscheduled visit that does not fall under any window will remain in the database and will be included in the listings.

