Enrolled subjects will be asked to complete a daily ePRO questionnaire to assess the severity of the 4 CS of CRS (nasal blockage/obstruction/congestion, facial pain/pressure, anterior/posterior nasal discharge, and loss of smell). In addition, the ePRO will capture use of daily saline irrigation by the subjects. Subjects will also complete 2 validated CRS-specific quality of life questionnaires, the SNOT-22 and CRS-PRO, at Screening, on Day 1 before treatment, and at Weeks 2, 4, 6, 8, 12, 16, and 20, at Week 24 before matrix removal, and at Week 28/EOS. CRS-PRO will also be assessed at Day 8 and Week 3. The PGIS will be administered on Day 1

(pretreatment) and at Weeks 8, 16, and 24/EOT. The PGIC will be assessed at Week 24/EOT. At Week 28/EOS visit, an end-of-study questionnaire will be administered.

Ethmoid cavity opacification will be assessed by CT scans obtained during Screening (or using a historical scan taken within 3 months of Screening) and at Week 25 visit, unless medically contraindicated. Subjects will be instructed to stop use of saline rinse approximately 24 hours prior to the scheduled sinus CT. Daily saline irrigation should then continue following the sinus CT. If a subject is experiencing or recovering from a cold, acute exacerbation of nasal allergy, or upper respiratory tract infection at Week 25 visit, the CT assessment should be performed 4 weeks after resolution of the adverse event. If a subject early terminates from the study or requires SCS or sinonasal surgery as rescue treatment during the study, every attempt should be made to perform the follow-up CT before subject receives the rescue treatment.

LYRA THERAPEUTICS, INC. STUDY LYR-220-2021-001

VERSION 4.0 (30 AUG2022)

Enrolled
jects
Sub
s for
Assessment
$\mathbf{0f}$
hedule
Sc
Ξ
Table

		2															
		_						Treat	Treatment Stage	age						Post-	4
Evaluation	ing & Run-In	dure Day														Treatment Stage	ient je
Visits #	1	2	3	~	4		⊢	⊢	5	⊢	F	9	7/7	F	œ	6	10/T p
Study Day/Week	DAY - DAY - 28 (Day - 28 to Day 0)	DAY 1 (Day 1)	DAY 2 (Day 2)	DAY 3 (Day 3)	DAY 5 (Day 5)	DAY 8 (Day 8)	WK 2 (Day 15±1)	WK 3 (Day 22±2)	WK 4 (Day 29±3)	WK 6 (Day 43±3)	WK 8 (Day 57±3) ª	WK 12 (Day 85±3)	WK 16 (Day 113±3) ª	WK 20 (Day 141±3) ª	WK 24/EO T/ET (Day 169±7)	WK 25 (5-9 days after T)	WK 28 (EOS) (25-31 days after EOT)
Informed Consent	×c																
Demographics	×																
Medical History	Х																
Vital Signs	Х																

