# 3.1.2.1 Analysis Visit Windows for Efficacy Endpoints

Table 1a. Visit Windows for SNOT-22

Analysis Visit	Target Analysis Day	Low Analysis Day	High Analysis Day
Week 2	Aday 15	Aday 2	Aday 21
Week 4	Aday 29	Aday 22	Aday 35
Week 6	Aday 43	Aday 36	Aday 49
Week 8	Aday 57	Aday 50	Aday 70
Week 12	Aday 85	Aday 71	Aday 98
Week 16	Aday 113	Aday 99	Aday 126
Week 20	Aday 141	Aday 127	Aday 154
Week 24	Aday 169	Aday 155	Aday 182
Week 28/follow-up*	Aenday 28	Aenday 1	Aenday 31

\* post-treatment follow-up.

Table 1b. Visits for Weekly 3CS and 4 Individual Cardinal Symptom Scores

Analysis Visit	Analysis Week (Days)
Week 1	Aday 2 - Aday 8
Week 2	Aday 9 - Aday 15
Week 3	Aday 16 - Aday 22
Week 4	Aday 23 - Aday 29
Week 5	Aday 30 - Aday 36
Week 6	Aday 37 - Aday 43
Week 7	Aday 44 - Aday 50
Week 8	Aday 51 - Aday 57
Week 9	Aday 58 - Aday 64
Week 10	Aday 65 - Aday 71
Week 11	Aday 72 - Aday 78
Week 12	Aday 79 - Aday 85
Week 13	Aday 86 - Aday 92
Week 14	Aday 93 - Aday 99
Week 15	Aday 100 - Aday 106
Week 16	Aday 107 - Aday 113
Week 17	Aday 114 - Aday 120
Week 18	Aday 121 - Aday 127
Week 19	Aday 128 - Aday 134
Week 20	Aday 135 - Aday 141
Week 21	Aday 142 - Aday 148
Week 22	Aday 149 - Aday 155

Week 23	Aday 156 - Aday 162	
Week 24	Aday 163 - Aday 169	
Week 25/follow-up*	Aenday 1 - Aenday 7	
Week 26/follow-up*	Aenday 8 - Aenday 14	
Week 27/follow-up*	Aenday 15 - Aenday 21	
Week 28/follow-up*	Aenday 22 - Aenday 28	

Note: score for a week is the average of the non-missing daily scores over the 7-day period of the week. If less than 4 daily scores are available for a week, the individual CS score will be considered missing for that week.

Table 1c. Visit Windows for CRS-PRO

Analysis Visit	Target Analysis Day	Low Analysis Day	High Analysis Day
Week 2	Aday 15	Aday 12	Aday 18
Week 3	Aday 22	Aday 19	Aday 25
Week 4	Aday 29	Aday 26	Aday 35
Week 6	Aday 43	Aday 36	Aday 49
Week 8	Aday 57	Aday 50	Aday 70
Week 12	Aday 85	Aday 71	Aday 98
Week 16	Aday 113	Aday 99	Aday 126
Week 20	Aday 141	Aday 127	Aday 154
Week 24	Aday 169	Aday 155	Aday 182
Week 28/follow-up*	Aenday 28	Aenday 1	Aenday 31

\* post-treatment follow-up.

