## Intercurrent events (ICE) and strategy

- (1) ICE1: Rescue treatment: efficacy data collected after rescue treatment will not be used (Hypothetical Strategy)
- (2) ICE2: Premature treatment discontinuation: efficacy data collected after treatment discontinuation will be included in the analysis regardless of attribution to treatment (Treatment Policy Strategy)

If both ICE1 and ICE2 occur for the same subject, addressing ICE1 takes precedence over ICE2. For example, if a subject took rescue medication at Week 10, and subsequently dropped out at Week 12 with no score at Week 24, then the method addressing ICE1 will be used.

3.4.2.1.2 Statistical Analysis for CFBL in SNOT-22 Total and Subdomain Scores 3.4.2.1.2.1 Part 1

Descriptive summary statistics on the values and changes from baseline will be presented for the SNOT-22 total and subdomain score at each analysis visit by treatment group.

3.4.2.1.2.2 Part 2

Statistical analysis of the CFBL in SNOT-22 total and subdomain scores at Weeks 2, 4, 6, 8, 12, 16, 20, 24, and 28/Follow-up will be carried out based on the Efficacy Analysis Set.

MMRM model without imputation: analysis will be carried out using MMRM model with the CFBL in SNOT-22 score as the dependent variable, and include the fixed, categorical effects of treatment, visit, treatment-by-visit interaction, and nasal polyp stratum as well as the continuous, fixed covariates of baseline score and baseline scoreby-visit interaction. An unstructured covariance structure shared across treatment groups will be used to model the within-subject errors. The covariance parameters in the above model will be fitted through a working model that assumes joint multivariate normality (MVN) of responses by maximizing the restricted likelihood (REML) under the working model, and the mean parameters will be estimated by generalized least squares after plugging in REML estimate of covariance parameters. In case the model does not converge with the unstructured covariance structure, the heterogenous Toeplitz structure (TOEPH) will be used instead. In case the model will not converge with the TOEPH structure, heterogenous compound symmetry (CSH) will be used instead. The Kenward-Roger approximation will be used to estimate denominator degrees of freedom and adjust nominal standard errors based on the inverse observed information from the working MVN model. Missing data will be handled by the MMRM under the missing at random (MAR) assumption.

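### The SAP windows Week 28 by days since end of treatment with no minimum study day, so an unrescued early terminator's end-of-study SNOT-22 or CRS-PRO score is analysed as Week 28 at whatever study week it was collected

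*SAP*

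**What the plan says.** SAP 3.1.1 sets up two clocks. Aday "will be calculated from the date of study treatment (LYR-220 or sham) administration", with that day as Aday 1. For the second, "analysis day relative to the last dose day (i.e., 'Aenday') will be calculated from the date of last dose of study treatment", with that day as Aenday 0. The same section adds: "Data collected up to 31 days after end of treatment will be included in the analysis".

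SAP 3.1.2 then gives the follow-up definition: "Follow up visits are defined as any visits during 1 day and up to 31 days after end of treatment". In "Table 1a. Visit Windows for SNOT-22" (SAP 3.1.2.1) and in Table 1c for CRS-PRO, every visit through Week 24 has an Aday window. Week 28/follow-up has only an Aenday window: 1 to 31, target 28, footnoted as post-treatment follow-up. On labels, SAP 3.1.2 says: "Scheduled visits will be assigned to analysis visits as recorded on the Case Report Form (CRF) if they are within the corresponding analysis visit windows".

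The schedule in Protocol 8.1 heads the last visit column "WK 28 (EOS) (25-31 days after EOT". Protocol 4.1.2 and 4.3 ask subjects who stop treatment early for the end-of-treatment, Week 25 and end-of-study (EOS) assessments. They schedule no return at calendar Week 24.

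SAP 2.3.3 and 3.4.2.1.1 define the endpoints as change from baseline at named weeks, including 24 and 28. For premature treatment discontinuation the strategy is that "efficacy data collected after treatment discontinuation will be included in the analysis regardless of attribution to treatment (Treatment Policy Strategy".

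**The concern.** Nothing in the follow-up definition or the tables requires treatment to have lasted about 24 weeks before a visit can count as Week 28. An early terminator's EOS visit carries the Week 28 label on the CRF, falls inside Aenday 1-31, and so keeps that label.

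A treatment-policy strategy uses the outcome at the time it was measured. Here the score is moved to another time. The Week 28 estimate then mixes scores from different calendar times, and the visit at which the score was actually taken may be left empty. Weeks 24 and 28 are also the two time points of the SNOT-22 ANCOVA analyses. In an MMRM with unstructured covariance, an off-time Week 28 value also informs the Week 24 estimate through the within-subject correlation.

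**Working it through.** **Inputs**
- Windows (SAP Tables 1a and 1c, identical from Week 6 on): Week 8 = Aday 50-70; Week 12 = 71-98; Week 16 = 99-126; Week 20 = 127-154; Week 24 = 155-182 (target 169); Week 28/follow-up = Aenday 1-31 (target 28).
- EOS visit: 25 to 31 days after end of treatment (Protocol 8.1).
- Assumption: end of treatment is the day of the ET visit. The SAP does not define last dose for a matrix placed once.

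**Formula:** Aday of EOS = Aday of ET + 25 to 31 (target + 28).

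**1. The plan's own figure.** With treatment ending on Aday 169, Aenday 28 is 169 + 28 = 197 = 28 × 7 + 1. The Week 28 label is correct for subjects treated to Week 24.

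**2. Earlier ends of treatment**

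| ET (Aday) | EOS Aday (target) | Window by Aday | SAP label | Weeks before Aday 197, at target |
|---|---|---|---|---|
| 29 | 54-60 (57) | Week 8 | Week 28 | (197 − 57)/7 = 20 |
| 57 | 82-88 (85) | Week 12 | Week 28 | (197 − 85)/7 = 16 |
| 85 | 110-116 (113) | Week 16 | Week 28 | (197 − 113)/7 = 12 |
| 113 | 138-144 (141) | Week 20 | Week 28 | (197 − 141)/7 = 8 |
| 141 | 166-172 (169) | Week 24 | Week 28 | (197 − 169)/7 = 4 |

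For ET on Day 57 the score is 197 − 88 = 109 to 197 − 82 = 115 days early.

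**3. When Week 24 is affected**
- The EOS target lies in Aday 155-182 for ET from 155 − 28 = 127 to 182 − 28 = 154. Every permitted EOS day lies there for ET from 155 − 25 = 130 to 182 − 31 = 151. In this range the ET visit itself is too early to count as Week 24.
- ET on Day 141: the EOS target is Day 169, the Week 24 target day, but the score is filed as Week 28. Week 24 is missing in the MMRM. For SNOT-22, the LOCF ANCOVA fills it with an earlier score (Day 141) although a Day 169 score exists. CRS-PRO has only the MMRM without imputation.
- ET on or before Day 123: 123 + 31 = 154, so nothing within 31 days reaches the Week 24 window, and no Week 24 score is scheduled.
- ET from Day 155, within the window: the ET visit itself counts as Week 24.

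**4. The 31-day limit.** With ET on Day 57, Day 169 is Aenday 169 − 57 = 112. A Day 169 score would be excluded under SAP 3.1.1 even if collected, despite the treatment-policy strategy.

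**5. Cardinal symptoms.** Table 1b has the same change of clock. With ET on Day 57, daily scores on Days 58-64 fit both Week 9 (Aday) and Week 25/follow-up (Aenday 1-7), and no precedence is stated.

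**6. Sensitivity to the assumption.** The SAP 3.3.9 heading counts exposure up to removal or dislodgement, and Protocol 4.1.2 allows the ET visit up to 7 days after the second dislodgement. Counted from dislodgement, EOS falls on Aenday 25 to 31 + 7 = 38, and visits after Aenday 31 would not keep the Week 28 label. If last dose were read literally as Day 1, the follow-up window would be Aday 2-32, which cannot be intended.

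**7. Size, illustration only.** The documents give no early-termination rate. Assume k = 1 to 4 of 20 subjects in an arm are affected, and a 10-point SNOT-22 difference between the true and labelled times. The share of off-time scores is k/20 = 5% to 20%, and the raw Week 28 arm mean moves by k/20 × 10 = 0.5 to 2.0 points. The SAP's minimal clinically important difference is 9.

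**The case against.** The strongest defence is that the window follows the protocol, which describes this visit as a 4-week post-treatment follow-up, and that the SAP footnotes it as such. Aligning an off-treatment assessment on time since removal is defensible. That stands in part: this is a disclosed choice, not a coding slip. But the footnote does not make a Day 85 score a Week 28 value in models whose endpoint is change at named weeks. Nor does it justify an empty or carried-forward Week 24 when a Day 169 score exists.

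Exposure is also limited. Post-rescue scores are unused in the main MMRM and replaced by the subject's worst score in the imputation analyses, so only unrescued early terminators matter. Efficacy is secondary and the trial is not powered for it.

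A reader might infer that every early terminator loses a true Week 24 score. The documents do not support that: subjects who stop by Day 123 have none scheduled. Their Week 24 gap comes from the visit schedule and the 31-day limit, not from the follow-up label.

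A reader might also infer a bias between arms. Spontaneous dislodgement can occur only with LYR-220, so imbalance is plausible. But Protocol 6.5 lets sham subjects have an early sham removal on request, and no rates are given, so it is not shown.

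**Conclusion.** The point holds with limits. If end of treatment is the ET visit, the SAP's rule analyses an unrescued early terminator's EOS SNOT-22 or CRS-PRO score as Week 28 whatever its calendar time: 16 weeks early at target for ET on Day 57. Misfiling of a score on or near the Week 24 target day is confined to ET at about Days 127-154. Both results conflict with the by-week endpoints and the treatment-policy strategy. The size cannot be computed from the documents; the 0.5 to 2 points shown rests wholly on assumed inputs. The rule should be corrected, but on a secondary, unpowered set of endpoints it does not threaten the trial's main objective.

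**What to change.** In SAP 3.1.1, 3.1.2 and Tables 1a to 1c:

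1. Use the Aenday-based Week 28/follow-up window only when treatment ended at Aday 155 or later. State which window wins where it overlaps Week 24.
2. For earlier terminations, assign all post-ET SNOT-22 and CRS-PRO scores by Aday. Add an Aday-based Week 28 window starting at Aday 183 (target 197). Without it, ET on Days 152-154 can put EOS on Days 183-185 (154 + 31 = 185), outside every window. An upper limit is also needed; Aday 207 is the latest EOS day for a subject on schedule (169 + 7 + 31).
3. Apply the same condition to the follow-up weeks in Table 1b.
4. Define end of treatment and last dose for a once-placed matrix and for sham, covering removal, dislodgement and the ET visit.
5. Reconcile the 31-day data limit with the treatment-policy strategy: either lift it for early terminators or state in the estimand that later data are not used.
6. Show the score 4 weeks after early removal as a separate descriptive row.

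The cost is a few sentences and a programming condition. The real downside is fewer Week 28 values: in the MMRM, most early terminators' Week 28 would be handled under missing at random, informed largely by subjects treated to Week 24. In the LOCF ANCOVA their Week 28 value would usually not change, because the same EOS score is carried forward; only Week 24 would.

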## Table 2b. Visit Windows for Nasal Endoscopy Assessments

Analysis Visit	Target Analysis Day	Low Analysis Day	High Analysis Day
Week 4	Aday 29	Aday 2	Aday 56
Week 12	Aday 85	Aday 57	Aday 126
Week 24	Aday 169	Aday 127	Aday 196
Week 25/follow-up*	Aenday 7	Aenday 1	Aenday 31
post-treatment follow-up.			

Table 2c. Visit Windows for IOP Assessments

Analysis Visit	Target Analysis Day	Low Analysis Day	High Analysis Day
Week 4	Aday 29	Aday 2	Aday 56
Week 12	Aday 85	Aday 57	Aday 196
Week 25/follow-up*	Aenday 7	Aenday 0	Aenday 31

\* post-treatment follow-up.

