# 3.1.3 Definition of Baseline

For cardinal symptoms (3CS and individual symptoms) and loss of smell score, the baseline is the average of non-missing daily scores over the 7-day period prior to and including Day 1. For other efficacy and safety assessments, the baseline is the last non-missing measurements prior to or on the day of treatment administration.

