#### 3.6.3 Nasal Endoscopy Assessments

Ethmoid cavities will be assessed by endoscopy during Screening, on Day 1 prior to LYR-220 administration/sham procedure, and at Week 4, 12, 24 (before LYR-220/sham removal), and 25/Follow Up visits.

Local safety evaluation of ethmoid cavity will be performed on Day 1 prior to LYR-220 administration/Sham procedure and at Week 4, 12, 24, and 25/Follow Up visits to document presence of epistaxis, mucosal injury, and any other adverse local observations in ethmoid cavity.

The severity of epistaxis will be determined by the Investigator on the basis of his or her clinical judgment and the following definitions:

- Mild: blood-tinged mucus, nonactive nose bleeding
- Moderate: active nose bleeding that does not require medical intervention
- Severe: frank nose bleeding that requires medical intervention

The severity of mucosal injury will be determined by the Investigator because of his or her clinical judgment and the following definitions:

- Mild: evidence of epithelial erosion
- Moderate: evidence of ulceration through the epithelial layer with exposed underneath tissue

Severe: perforation

Counts and percentages of subjects will be presented at baseline for the following:

- Severity of Epistaxis (Left): [MILD | MODERATE | SEVERE | NA]
- Severity of Epistaxis (Right): [MILD | MODERATE | SEVERE | NA]
- Severity of Mucosal injury (Left): [MILD | MODERATE | SEVERE | NA]
- Severity of Mucosal injury (Right): [MILD | MODERATE | SEVERE | NA]

Newly identified or worsened endoscopic findings will be presented at each scheduled visit and in overall.

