#### 3.6.5 Ophthalmologic Assessments

The ophthalmologic assessment of IOP and slit-lamp examination to identify development or worsening of cataract will be conducted at Screening and Week 25/Follow Up visits. The cataract assessment will be conducted according to the Simplified Cataract Grading System authored by the World Health Organization (WHO) Cataract Grading Group. Subject's eyes will be dilated with mydriatics following the WHO guidance for cataract assessment. IOP may be measured using Goldmann applanation tonometer, noncontact tonometer, or tono-pen; however, it is recommended that the same method be used for consistency across serial assessments on a given subject. IOP assessment will also be performed at Week 4 and 12 visits. Assessments will be conducted by an ophthalmologist/optometrist who is blinded to the subject's treatment assignment.

The number and percentage of subjects with clinically significant increase of IOP will be presented by visit and in overall. Descriptive summary statistics on the values and change from base line of IOP will be presented by visit.

The number and percentage of subjects with newly identified or worsened cataract will be presented by visit and in overall.

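### SAP 3.1.2 keeps one visit per window for safety endpoints too, so IOP and endoscopy events seen only at extra visits can drop out of the through-Week-25 counts

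*SAP*

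**What the plan says.** SAP 3.1.2 sets the scope: "Analysis visits will be used for efficacy and safety endpoint analysis". Extra visits enter the same scheme, since "results from unscheduled visits will be assigned to analysis visits according to the following visit windows". So do scheduled visits that miss their own window: "Scheduled visits that do not fall in the corresponding analysis visit windows are considered unscheduled visits when assigning analysis visits". One record per window then survives: "When multiple visits are within the same analysis visit window, the one closest to the target day will be used". The tie rule that follows covers efficacy only, and an unscheduled visit that fits no window goes to listings only.

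The safety windows in SAP 3.1.2.2 (Tables 2a to 2c) are:

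| Assessment | Week 4 | Week 12 | Week 24 | Week 25/Follow Up |
|---|---|---|---|---|
| Endoscopy | Aday 2–56 | Aday 57–126 | Aday 127–196 | Aenday 1–31 |
| IOP | Aday 2–56 | Aday 57–196 | none | Aenday 0–31 |
| Slit-lamp | none | none | none | Aenday 0–31 |

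SAP 2.3.2 defines the IOP, endoscopy and cataract endpoints as events occurring through Week 25/Follow Up. For reporting, 3.6.5 says "The number and percentage of subjects with clinically significant increase of IOP will be presented by visit and in overall", and 3.6.3 says "Newly identified or worsened endoscopic findings will be presented at each scheduled visit and in overall". Neither section states which records feed the overall row.

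**The concern.** Choosing the visit nearest a target day suits by-visit means, where each subject should contribute one comparable value. It does not suit an endpoint that asks whether an event ever happened, because it selects on date and ignores the value. If a normal scheduled reading and an abnormal extra reading share a window, the abnormal one is set aside.

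Extra examinations are foreseen. Protocol 6.3 refers to endoscopy at unscheduled visits, and Protocol 4.1.2 requires every early-termination (ET) visit to include the Week 24/EOT assessments, which include endoscopy. Safety is part of the study's stated main purpose (SAP 2.2.5), and each arm is small enough for one subject to change the reported picture.

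**Working it through.** The plan gives no figure for this point, so there is none to reproduce. The check applies the 3.1.2 rule day by day.

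**Inputs.** Windows as tabulated above. Targets are Aday 29, 85 and 169. Visit tolerances are ±3 days at Weeks 4 and 12 and ±7 days at Week 24 (Protocol Table 1).

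**Rule.** An extra visit on day d loses when |d − target| is greater than the scheduled visit's own distance from target.

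| Window | Days in window | Extra visit loses, scheduled visit on target | Extra visit loses, scheduled visit at edge of tolerance |
|---|---|---|---|
| IOP Week 4 | 56 − 2 + 1 = 55 | 54 (98%) | 48 (87%) |
| IOP Week 12 | 196 − 57 + 1 = 140 | 139 (99%) | 133 (95%) |
| Endoscopy Week 4 | 55 | 54 (98%) | 48 (87%) |
| Endoscopy Week 12 | 126 − 57 + 1 = 70 | 69 (99%) | 63 (90%) |
| Endoscopy Week 24 | 196 − 127 + 1 = 70 | 69 (99%) | 55 (79%) |

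**Restricted to time on treatment.** With removal on Day 169, Aday 2–168 is 167 days. An extra IOP reading loses on 153 to 165 of them (92–99%), and an extra endoscopy on 146 to 165 (87–99%). For IOP the main exposure is after Week 12. No IOP is scheduled again until Week 25, so after a Day 85 visit any reading on Aday 86–168 (168 − 86 + 1 = 83 days) loses.

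**An ET endoscopy at Aday 100.** It lies outside the Week 24 window (127–196), so it becomes unscheduled. It falls in Week 12 (57–126) at distance |100 − 85| = 15. A Week 12 endoscopy on Aday 82–88 is at distance 3 or less and is kept. If removal that day is Aenday 0 (an assumption), the follow-up window, which starts at Aenday 1, does not recover it. With a Day 85 visit, the same happens to an ET endoscopy on any day from 86 to 126.

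**Slit-lamp.** The only post-baseline window starts at Aenday 0. An unscheduled on-treatment result therefore fits no window and is only listed.

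**Size.** Part 2 plans about 20 subjects on LYR-220-32. SAP 3.1 pools the Part 1 subjects who received that design, and Part 1 has at most 10 subjects in all, so n lies between about 20 and 30. One missed subject is 1/20 = 5.0 points or 1/30 = 3.3 points.

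The documents give no rate of events seen only at a non-selected visit. For an assumed rate p, the chance of missing at least one subject is 1 − (1 − p)^n:

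| p | n = 20 | n = 30 |
|---|---|---|
| 2% | 33.2% | 45.5% |
| 5% | 64.2% | 78.5% |
| 10% | 87.8% | 95.8% |

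**The case against.** The strongest reply is that loss is not established. The overall rows are underived, the endoscopy and cataract definitions in SAP 3.1.4 refer to post-baseline visits in general, and the IOP definition carries no visit limit. A programmer could build the overall rows from all records. That stands, and it limits the conclusion. It does not remove the problem, because 3.1.2 is the only selection rule given and it expressly covers safety endpoints.

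Other outputs also limit the harm. All data are listed (SAP 6). Findings reported as adverse events appear in tables that do not depend on visit windows (SAP 3.6.1). The primary endpoint, product-related serious events, is unaffected. A finding that persists to Week 25 would be counted there.

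A reader might infer more than the documents support:

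- **That every other IOP in the 140-day window is dropped.** With removal on Day 169 ± 7 and Week 25 falling 5–9 days later, the Week 25 IOP falls on about Day 167–185 (162 + 5 to 176 + 9), inside Aday 57–196, but is kept under its own follow-up window. With removal on Day 169, the on-treatment part of the window is 168 − 57 + 1 = 112 days.
- **That LYR-220 events are hidden more often than sham events.** No unscheduled-visit rates by arm are given. Extra visits need not signal an abnormal reading either: dislodgement and a subject's request for removal can also lead to an ET visit.
- **That a post-insertion finding becomes the baseline.** SAP 3.1.3 does say "the baseline is the last non-missing measurements prior to or on the day of treatment administration", but Protocol 8.3.4 and SAP 3.6.3 place the Day 1 endoscopy before the procedure, and no IOP is scheduled that day. This is at most a wording clarification.
- **That each missed subject costs exactly 5 points.** That ignores the Part 1 pooling.

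**Conclusion.** The concern holds as follows. Read as written, SAP 3.1.2 leaves an IOP or endoscopy event out of its through-Week-25 endpoint when the event is seen only at an unscheduled or ET visit and an on-time scheduled visit shares the window. Once such a visit occurs, exclusion is close to automatic (87–99% of on-treatment days). An on-treatment unscheduled slit-lamp result has no window at all.

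This is where the text leads; it is not a certain undercount, because the overall rows are not derived anywhere. An extra visit is kept when it is the only visit in its window or the closest to target. Each missed subject moves the LYR-220-32 rate by about 3.3 to 5 percentage points, for n between 30 and 20. How many would be missed is unknown, and the probabilities above are illustrative. The ET example assumes that end of treatment is dated to the removal visit. If it were dated to an earlier dislodgement, the ET endoscopy would fall in the follow-up window and compete there with the Week 25 visit.

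**What to change.** - In SAP 3.1.2, limit the closest-to-target rule to efficacy scores and by-visit descriptive safety summaries, and add a tie rule for safety that takes the worse value.
- In 3.6.3 and 3.6.5, state that the overall counts of clinically significant IOP increase and of new or worsened endoscopic findings use every post-procedure record through Week 25/Follow Up, whether scheduled, unscheduled or ET, taking the worst value per subject.
- Apply the same rule to new or worsened cataract.
- Footnote the tables to say that overall counts may exceed what the by-visit rows show.
- Optionally, in 3.1.3, say that the safety baseline is the last value before the procedure.

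The cost is SAP wording and programming, with no new data collection. The reported event rates may come out slightly less favorable.
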